8.3 Reasons for Removal From Treatment or Study

8.3.1 Reasons for Removal From Treatment

Reasons for removal from the investigational product include any of the following:

- subject request
- safety concern (eg, due to an adverse event)
- ineligibility determined
- protocol deviation
- non-compliance (eg, procedural or dosing as defined in [Section 6.2.1.1](#))
- requirement for alternative therapy
- pregnancy

- decision by Amgen (other than subject request, safety concern, or lost to follow-up)
- decision by investigator (other than subject request, safety concern, or lost to follow-up)
- death
- lost to follow-up
- Confirmed Disease Progression per IMWG ([Appendix D](#))

8.3.2 Reasons for Removal From Study

Reasons for removal of a subject from the study are:

- decision by Amgen
- withdrawal of consent from study
- death
- lost to follow-up

9. SAFETY DATA COLLECTION, RECORDING, AND REPORTING

9.1 Definition of Safety Events

9.1.1 Adverse Events

An adverse event is defined as any untoward medical occurrence in a clinical trial subject. The event does not necessarily have a causal relationship with study treatment. The investigator is responsible for ensuring that any adverse events observed by the investigator or reported by the subject are recorded in the subject's medical record.

The definition of adverse events includes worsening of a pre-existing medical condition. Worsening indicates that the pre-existing medical condition or underlying disease (eg, diabetes, migraine headaches, gout) has increased in severity, frequency, and/or duration more than expected by the investigator's assessment. A pre-existing condition that has not worsened more than anticipated (ie, more than usual fluctuation of disease) during the study or involves an intervention such as elective cosmetic surgery or a medical procedure while on study, is not considered an adverse event.

If the severity of an adverse event worsens from the date of onset to the date of resolution, record a single event for each increased level of severity on the Event eCRF.

For situations when an adverse event or serious adverse event is due to multiple myeloma report all known signs and symptoms. Death due to disease progression in the absence of signs and symptoms should be reported as the primary tumor type (eg, multiple myeloma).

Approved

Note: The term “disease progression” should not be used to describe the adverse event.

The investigator’s clinical judgment is used to determine whether a subject is to be removed from treatment due to an adverse event. In the event a subject, or subject’s legally acceptable representative requests to withdraw from protocol-required therapy or the study due to an adverse event, refer to [Section 8.1](#) for additional instructions on the procedures recommended for safe withdrawal from protocol-required therapy or the study.

9.1.2 Serious Adverse Events

A serious adverse event is defined as an adverse event that meets at least 1 of the following serious criteria:

- fatal
- life threatening (places the subject at immediate risk of death)
- requires in patient hospitalization or prolongation of existing hospitalization
- results in persistent or significant disability/incapacity
- congenital anomaly/birth defect
- other medically important serious event

An adverse event would meet the criterion of “requires hospitalization”, if the event necessitated an admission to a health care facility (eg, overnight stay).

If an investigator considers an event to be clinically important, but it does not meet any of the serious criteria, the event could be classified as a serious adverse event under the criterion of “other medically important serious event”. Examples of such events could include allergic bronchospasm, convulsions, blood dyscrasias, drug induced liver injury (DILI) (see [Appendix A](#) for DILI reporting criteria), or events that necessitate an emergency room visit, outpatient surgery, or urgent intervention.

9.2 Safety Event Reporting Procedures

9.2.1 Adverse Events

9.2.1.1 Reporting Procedures for Adverse Events That do not Meet Serious Criteria

The investigator is responsible for ensuring that all adverse events observed by the investigator or reported by the subject that occur after first dose of investigational product through the end of study 30 to 37 days after the last dose of investigational product are reported using the Event eCRF.

The investigator must assign the following adverse event attributes:

- Adverse event diagnosis or syndrome(s), if known (if not known, signs or symptoms),
- Dates of onset and resolution (if resolved),
- Severity [and/or toxicity per protocol],
- Assessment of relatedness to investigational product, and
- Action taken.

The adverse event grading scale used will be the Common Terminology Criteria for Adverse Events (CTCAE) version 4.0. The grading scale used in this study is described in [Appendix A](#). The investigator must assess whether the adverse event is possibly related to the investigational product. This relationship is indicated by a “yes” or “no” response to the question: Is there a reasonable possibility that the event may have been caused by the investigational product? If the severity of an adverse event changes from the date of onset to the date of resolution, record a single event for each level of severity on the Adverse Event Summary eCRF.

The investigator must assess whether the adverse event is possibly related to any study mandated activity (eg, administration of investigational product and/or procedure (including any screening procedures). This relationship is indicated by a “yes” or “no” response to the question: “Is there a reasonable possibility that the event may have been caused by a study activity (eg, administration of investigational product, and/or procedure”?

The investigator is responsible for reviewing laboratory test results and determining whether an abnormal value in an individual study subject represents a clinically significant change from the subject’s baseline values. In general, abnormal laboratory findings without clinical significance (based on the Investigator’s judgment) are not to be recorded as adverse events. However, laboratory value changes that require treatment or adjustment in current therapy are considered adverse events. Where applicable, clinical sequelae (not the laboratory abnormality) are to be recorded as the adverse event.

The investigator is expected to follow reported adverse events until stabilization or reversibility.

9.2.1.2 Reporting Procedures for Serious Adverse Events

The investigator is responsible for ensuring that all serious adverse events observed by the investigator or reported by the subject that occur after signing of the informed

consent through 30 to 37 days after the last dose of investigational product are recorded in the subject's medical record and are submitted to Amgen. All serious adverse events must be submitted to Amgen within 24 hours following the investigator's knowledge of the event via the Event eCRF.

9.2.1.3 Reporting Serious Adverse Events After the Protocol-required Reporting Period

There is no requirement to monitor study subjects for serious adverse events following the protocol-required reporting period or after end of study. However, these serious adverse events can be reported to Amgen. In some countries (eg, European Union [EU] member states), investigators are required to report serious adverse events that they become aware of after end of study. If serious adverse events are reported, the investigator is to report them to Amgen within 24 hours following the investigator's knowledge of the event.

Serious adverse events reported outside of the protocol-required reporting period will be captured within the safety database as clinical trial cases for the purposes of expedited reporting.

If the electronic data capture (EDC) system is unavailable to the site staff to report the serious adverse event, the information is to be reported to Amgen via an electronic Serious Adverse Event (eSAE) Contingency Report Form within 24 hours of the investigator's knowledge of the event. See [Appendix B](#) for a sample of the Serious Adverse Event Worksheet /electronic Serious Adverse Event Contingency Report Form. For EDC studies where the first notification of a Serious Adverse Event is reported to Amgen via the eSerious Adverse Event Contingency Report Form, the data must be entered into the EDC system when the system is again available.

The investigator is expected to follow reported serious adverse events until stabilization or reversibility.

New information relating to a previously reported serious adverse event must be submitted to Amgen. All new information for serious adverse events must be sent to Amgen within 24 hours following knowledge of the new information. The investigator may be asked to provide additional follow up information, which may include a discharge summary or extracts from the medical record. Information provided about the serious adverse event must be consistent with that recorded on the Event eCRF.

Approved

Amgen will report serious adverse events and/or suspected unexpected serious adverse reactions as required to regulatory authorities, investigators/institutions, and IRBs/IECs in compliance with all reporting requirements according to local regulations and good clinical practice.

9.3 Pregnancy and Lactation Reporting

If a pregnancy occurs in a female subject, or female partner of a male subject, while the subject is taking protocol-required therapies report the pregnancy to Amgen as specified below.

In addition to reporting any pregnancies occurring during the study, investigators should monitor for pregnancies that occur after the last dose of protocol-required therapies through 3 months after the last dose of investigational product.

The pregnancy should be reported to Amgen's Global Patient Safety within 24 hours of the investigator's knowledge of the event of a pregnancy. Report a pregnancy on the Pregnancy Notification Worksheet ([Appendix C](#)). Amgen Global Patient Safety will follow-up with the investigator regarding additional information that may be requested.

If a female subject becomes pregnant during the study, the investigator should attempt to obtain information regarding the birth outcome and health of the infant.

If the outcome of the pregnancy meets a criterion for immediate classification as a Serious Adverse Event (eg, female subject experiences a spontaneous abortion, stillbirth, or neonatal death or there is a fetal or neonatal congenital anomaly) the investigator will report the event as a Serious Adverse Event.

If a lactation case occurs while the female subject is taking protocol-required therapies report the lactation case to Amgen as specified below.

In addition to reporting a lactation case during the study, investigators should monitor for lactation cases that occur after the last dose of protocol-required therapies through 3 months after the last dose of investigational product.

Any lactation case should be reported to Amgen's Global Patient Safety within 24 hours of the Investigator's knowledge of event. Report a lactation case on the Lactation Notification Worksheet ([Appendix C](#)). Amgen Global Patient Safety will follow-up with the investigator regarding additional information that may be requested.

Approved

If a male subject's female partner becomes pregnant, the investigator should discuss obtaining information regarding the birth outcome and health of the infant from the pregnant partner.

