3.5.1 Study Duration for Subjects

It is anticipated that each subject will be on study for approximately 2 weeks for screening and 6 months of treatment period. Approximately 30 to 37 days after the last dose of AMG 224, the subject will return to the clinic for a safety follow-up (EOS) visit. The estimated study duration for participant is 7.5 months but this may be longer or shorter depending on the subject’s disease, ability to tolerate AMG 224 and/or willingness to participate in the study.

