- 216 Hepatitis B and C based on the following results:
- Positive for hepatitis B surface antigen (HBsAg) (indicative of chronic hepatitis B or recent acute hepatitis B)
 - Negative HBsAg and positive for hepatitis B core antibody: hepatitis B virus DNA by polymerase chain reaction (PCR) is necessary. Detectable hepatitis B virus DNA suggests occult hepatitis B
 - Positive Hepatitis C virus antibody (HCVAb): hepatitis C virus RNA by PCR is necessary. Detectable hepatitis C virus RNA suggests chronic hepatitis C
- 217 Known positive results for Human Immunodeficiency Virus (HIV)
- 218 Unresolved toxicities from prior anti-tumor therapy, defined as not having resolved to Common Terminology Criteria for Adverse Events (CTCAE) version 4.0 grade 1, or to levels dictated in the eligibility criteria with the exception of grade 2 peripheral neuropathy, alopecia or toxicities from prior anti-tumor therapy that are considered irreversible (defined as having been present and stable for >4 weeks may be allowed if they are not otherwise described in the exclusion criteria AND there is agreement to allow by both the investigator and Amgen medical monitor).
- 219 Treatment with medications known to cause QTc interval prolongation (see [Appendix F](#)) within 7 days of study day 1 unless approved by the Amgen medical monitor.
- 220 A baseline ECG QTcF > 470 msec
- 221 Anti-tumor therapy (chemotherapy, antibody therapy, molecular targeted therapy, or investigational agent) within 28 days prior to study day 1.

Approved

- 222 Prior systemic radiation therapy must have been completed at least 28 days before study day 1. Prior focal radiotherapy completed at least 14 days before study day 1.
- 223 Major surgery within 28 days prior to study day 1.
- 224 Male and female of reproductive potential who are unwilling to practice a highly effective method(s) of birth control while on study through 3 months (female) or 6 months (male) after receiving the last dose of study drug. Acceptable highly effective methods of birth control are defined as those which result in a low failure rate (ie, less than 1% per year) when used consistently and correctly such as implants, injectables, combined oral contraceptives, intrauterine devices (IUDs), sexual abstinence or vasectomized partner. Barrier methods of contraception are acceptable if a condom with spermicide (male) is used in combination with diaphragm, cervical cap or cervical sponge (female).

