- 225 Female who are breastfeeding or who plan to breastfeed while on study through 3 months after receiving the last dose of study drug.
- 226 Female with a positive pregnancy test.
- 227 Female planning to become pregnant while on study through 3 months after receiving the last dose of study drug.
- 228 Subject has known sensitivity to any components of the investigational product.
- 229 History or evidence of any other clinically significant disorder, condition or disease that, in the opinion of the investigator or Amgen physician, if consulted, would pose a risk to subject safety or interfere with the study evaluation, procedures or completion

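### Pregnancy monitoring in section 9.3 stops at 3 months after the last dose, but criterion 224 sets male contraception through 6 months, so months 4 to 6 carry no duty to look for partner pregnancies

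*Protocol*

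**What the plan says.** Criterion 224 in Protocol section 4.2 excludes men and women of reproductive potential who will not use highly effective contraception "while on study through 3 months (female) or 6 months (male) after receiving the last dose of study drug". Criterion 227 uses the same 3-month period for women: "Female planning to become pregnant while on study through 3 months after receiving the last dose of study drug".

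Section 9.3 opens with pregnancies during treatment and names both groups: "If a pregnancy occurs in a female subject, or female partner of a male subject". For the time after treatment it asks investigators to "monitor for pregnancies that occur after the last dose of protocol-required therapies through 3 months after the last dose of investigational product". That sentence has one period and does not separate women from the partners of men. The section's last paragraph returns to partners: "If a male subject's female partner becomes pregnant, the investigator should discuss obtaining information regarding the birth outcome and health of the infant". It has no time limit.

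On contact after treatment, section 3.5.1 says that about 30 to 37 days after the last dose "the subject will return to the clinic for a safety follow-up (EOS) visit". Section 9.2.1.3 adds: "There is no requirement to monitor study subjects for serious adverse events following the protocol-required reporting period or after end of study".

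**The concern.** The protocol distinguishes the sexes when it says how long conception should be avoided, and does not when it says how long to watch for pregnancy. The single monitoring period equals the female contraception period and is half the male one. A site that follows section 9.3 as written may stop asking male subjects about partner pregnancy while the period named in criterion 224 is still running.

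This is a first-in-human study of a conjugate whose payload, DM1, blocks tubulin polymerisation and so cell division (sections 2.2 and 2.2.1). Partner exposures would be few, and each would be informative. A conception in months 4 to 6 after the last dose would reach the sponsor only if someone volunteered it. What is at stake is the completeness of safety follow-up. Pregnancy is not a study endpoint, and neither the estimate of the maximum tolerated dose nor any planned analysis uses it.

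**Working it through.** The plan gives no figure to reproduce. The check compares two time windows.

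**Inputs**

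| Item | Female subjects | Male subjects | Source |
|---|---|---|---|
| Contraception after last dose | 3 months | 6 months | Section 4.2, criterion 224 |
| Pregnancy monitoring after last dose | 3 months | 3 months (partners) | Section 9.3 |
| Last scheduled visit | day 30–37 | day 30–37 | Section 3.5.1 |
| Planned treatment | 6 months | 6 months | Section 3.5.1 |

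**Gap after the last dose** = contraception period − monitoring period

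- Women: 3 − 3 = 0 months.
- Men: 6 − 3 = 3 months, which is 3/6 = 50% of their post-dose period.

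**Share of the whole male contraception period.** Criterion 224 also covers time on study, when section 9.3 does apply. Counting from first dose, the share without a monitoring duty is 3/(T + 6), where T is months of treatment.

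- T = 6, the planned duration ("each subject will be on study for approximately 2 weeks for screening and 6 months of treatment period"): 3/12 = 25%.
- T ≈ 0, a single dose (assumed lower bound): 3/6 = 50%.
- T = 12 (assumed upper bound): 3/18 = 17%.

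These percentages describe time covered. They do not measure the risk of a pregnancy.

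**Does any other text fill months 4 to 6?**

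- *End-of-study visit.* It falls on day 30–37. With 3 months taken as about 90 days, month 4 begins at about day 91, which is 91 − 37 = 54 to 91 − 30 = 61 days after that visit.
- *Serious adverse events.* Section 9.2.1.3 requires no monitoring after the reporting period.
- *Partner paragraph in section 9.3.* It has no time limit, but it applies once a partner is known to be pregnant and concerns information on the outcome. It does not ask anyone to look.

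**Are partners covered by the 3-month sentence?** The sentence speaks only of pregnancies. Partners come in from the preceding paragraph, which names them. On the other reading they have no post-dose monitoring at all, and the gap for men is 6 − 0 = 6 months. The 3-month figure is therefore the more favourable reading.

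**The case against.** The strongest argument is that criterion 224 is an entry criterion. It tests willingness at enrolment and does not itself impose an obligation after treatment, and nothing in the documents says that the contraception and monitoring periods must be equal. This is true. But criterion 224 is the only statement in the available text of how long men should avoid conception, and the protocol gives no reason to stop looking halfway through.

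A second argument is that the pregnancy worksheet in Appendix C and the consent form could not be seen and may state 6 months. That limit stands. If either does, section 9.3 conflicts with it and still needs correcting.

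A third argument is practical. No contact is scheduled between the end-of-study visit and month 3 either, so the existing duty already runs without a visit behind it, and lengthening it may not detect many more pregnancies. This stands in part: the yield is uncertain. A stated duty still tells sites to keep asking, whereas the present text tells them when they may stop.

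Finally, reporting routes remain open. The 24-hour rule in section 9.3 runs from the investigator's knowledge of the pregnancy, and section 9.2.1.3 accepts late reports of serious adverse events. That is correct, and it confines the point to active monitoring.

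**Conclusion.** The mismatch is real in the current protocol text. For male subjects, 3 of the 6 months of contraception after the last dose (50%) have no instruction to monitor for partner pregnancy. At the planned 6 months of treatment this is 25% of the whole male period. For women the gap is 0.

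The conclusion assumes that the 3-month sentence includes partners; if it does not, the gap is larger. It also assumes that the unseen worksheet and consent text do not already set a longer period. The number of men with partners of reproductive potential is not given and is probably small in a study of about 60 subjects with at least three prior lines of therapy. The sponsor should correct it as a matter of safety surveillance; no statistical result changes.

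**What to change.** In section 9.3, replace the single post-dose period with two: pregnancies in female subjects are monitored and reported through 3 months after the last dose, and pregnancies in female partners of male subjects through 6 months. If the sponsor changes the contraception period in criterion 224, the monitoring period should be no shorter than the new one. Check the pregnancy worksheet and the consent text, and align them if they differ.

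This costs one sentence in the protocol and possible wording changes in those two documents. It adds no visit or test. The burden is three more months of pregnancy follow-up for male subjects, by whatever contact sites already use between the end-of-study visit and month 3.

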10. STATISTICAL CONSIDERATIONS

10.1 Study Endpoints, Analysis Sets, and Covariates

10.1.1 Study Endpoints

Primary Endpoints

- Safety: Incidence of DLTs, treatment-related, treatment-emergent adverse events and clinically significant changes in vital signs, physical examinations, ECGs and clinical laboratory tests

Secondary Endpoints

- PK profile: PK parameters for AMG 224 conjugated antibody, Total anti-BCMA antibody, and total unconjugated DM1 including, but not limited to maximum observed concentration (C_{max}), minimum observed concentration (C_{min}), area under the concentration-time curve (AUC), clearance (CL), and if feasible half-life ($t_{1/2}$)
- Overall response according to International Myeloma Working Group (IMWG) uniform response criteria, relative reduction in M-component, time to progression (TTP), duration of response (DOR)
- Conversion to MRD negativity
- Incidence of anti-AMG 224 antibody formation

Exploratory Endpoints

- Quantification of BCMA expression in pre-dose bone marrow biopsy and bone-marrow aspirates
- Pre-dose bone marrow biopsy and/or plasma DNA gene expression profiles.
- Serum level of BCMA, BCMA ligands, APRIL and BAFF
- Quantification of circulating tumor cells, plasma cells and/or BCMA specific tumor cells

